8.2.5 Clinical Safety Laboratory Assessments

Blood and urine samples for determination of clinical chemistry, haematology, coagulation, and urinalysis will be taken at the visits indicated in the SoA (Section 1.3).

Additional safety samples may be collected if clinically indicated at the discretion of the investigator. The date, time of collection and results (values, units and reference ranges) will be recorded on the appropriate eCRF.

The clinical chemistry, haematology including coagulation and urinalysis will be performed at a local laboratory at or near to the investigator site. Sample tubes and sample sizes may vary depending on laboratory method used and routine practice at the site.

Other safety laboratory tests include assessment for pregnancy (serum at screening or urine at other time points), HBsAg, HCV antibodies, and HIV antibodies. Pregnancy tests may be performed at the site using a licensed test (urine or serum pregnancy test). Women of childbearing potential are required to have a pregnancy test on Day 1 of every cycle and then as clinically indicated for studies with no suspected teratogenicity/foetotoxicity. Pregnancy test may occur on Day 1, but results must be available and reviewed by the treating physician or investigator prior to commencing study treatment. Abnormal clinically significant laboratory results should be repeated as soon as possible (preferably within 24 to 48 hours).

The following laboratory variables will be measured:

Table 14 Laboratory Safety Variables

Haematology/Haemostasis (whole blood)	Clinical chemistry (serum or plasma)
НЬ	Albumin
Leukocyte count (total white cell count) a	ALPc
Haematocrit	ALT ^c
Red blood cell count	AST ^c
Leukocyte differential count (absolute count)	Amylase ^d
Neutrophils ^a	Bicarbonate ^b
Lymphocytes ^a	Calcium, total or calcium corrected (for albumin)
Monocytes	Chloride ^b
Basophils	Conjugated bilirubin ^c
Eosinophils	Creatinine and CrCL ^b
Platelet count	C-reactive protein
	Gamma-glutamyl transferase
Coagulation parameters	Glucose (random)
PTT and INR ^b	Lactate dehydrogenase
Urinalysis (dipstick)	Lipase ^d
Glucose	Magnesium ^b
Protein	Phosphate
Blood	Potassium

Table 14 Laboratory Safety Variables

Colour and appearance	Protein, total
pH and specific gravity	Sodium
Bilirubin	TBL°
Ketones	TSH
	T3 free (reflex) ^e
Virology (serum): HBsAg, HCV and HIV antibodies f	T4 free (reflex) ^e
Pregnancy β-hCG in serum (pre-/screening) or urine (all other visits); only in WOCBP	Unconjugated bilirubin
	Urea nitrogen/blood urea nitrogen, depending on local practice

- ^a Can be recorded as absolute counts or as percentages. Total white cell count therefore has to be provided.
- Bicarbonate (where available), chloride, creatinine clearance, INR, magnesium and PTT testing are to be performed at baseline, on Day 1 (unless all screening laboratory clinical chemistry and haematology assessments are performed within 3 days prior to Day 1), and if clinically indicated. Creatinine clearance to be calculated using Cockcroft and Gault equation (Cockcroft and Gault 1976).
- Tests for ALT, AST, alkaline phosphatase, and total bilirubin must be conducted and assessed concurrently. If total bilirubin is ≥ 2 × upper limit of normal (and no evidence of Gilbert's syndrome), then fractionate into direct and indirect bilirubin.
- It is preferable that both amylase and lipase parameters are assessed. For sites where only 1 of these parameters is routinely measured, either lipase or amylase is acceptable.
- Free T3 or free T4 will only be measured if TSH is abnormal or if there is a clinical suspicion of an AE related to the endocrine system.
- If patient is HCV-Ag positive, then he/she should be checked for HCV RNA.

NB. In case a patient shows an AST or ALT \geq 3×ULN together with total bilirubin \geq 2×ULN please refer to Appendix E 'Actions required in cases of increases in liver biochemistry and evaluation of Hy's law', for further instructions.

AE = adverse event; ALP = alkaline phosphatase; ALT = alanine aminotransferase; AST = aspartate aminotransferase; CK = creatinine kinase; CrCL = creatinine clearance; HB = haemoglobin; INR = international normalised ratio; aPTT = activated partial thromboplastin time T3 = triiodothyronine; T4 = thyroxine; TBL = total bilirubin; TSH = thyroid-stimulating hormone; ULN=upper limit of normal.

Additionally, a serum (screening) or urine (other time points) sample will be collected for pregnancy testing from all women of childbearing potential at the visits indicated in the SoA (Section 1.3).

The investigator should assess the available results with regard to clinically relevant abnormalities in documentation. Any clinically significant abnormal laboratory values should be repeated as clinically indicated and recorded on the eCRF. Situations in which laboratory safety results should be reported as AEs are described in Section 8.3.5.

All patients with Grade 3 or 4 laboratory values at the time of completion or discontinuation from study treatment must be followed and have further tests performed until the laboratory values have returned to Grade 1 or 2, unless these values are not likely to improve because of the underlying disease.

8.2.6 Other Safety Assessments

8.2.6.1 Echocardiogram/Multigated Acquisition Scan

An echocardiogram or MUGA scan to assess LVEF will be performed at the visits as shown in SoA (Table 1, Table 2, and Table 3). The modality of the cardiac function assessments must be consistent for a given patient (ie, if echocardiogram is used for the screening assessment for a given patient, then echocardiogram should also be used for subsequent scans for that patient). The patient should also be examined using the same machine and operator whenever possible, and quantitative measurements should be taken (ie, accurate to 1% and not estimated to 5%).

If a patient has had an echocardiogram or MUGA performed within 4 weeks prior to treatment discontinuation, the discontinuation visit echocardiogram/MUGA scan is not required unless clinically indicated. If a patient has any clinically significant decrease in LVEF (greater than 10 percentage points to below 50%), there should be follow-up within 4 weeks until resolution.

Situations in which echocardiogram or MUGA results should be reported as AEs are described in Section 8.3.5.

8.2.6.2 Pneumonitis (Interstitial Lung Disease) Investigation

If new or worsening pulmonary symptoms (eg, dyspnoea) or radiological abnormality suggestive of pneumonitis/ILD is observed, toxicity management as described in detail in the Dosing Modification and Toxicity Management Guidelines (see the Annex document to this CSP) will be applied. The results of the full diagnostic workup (including high-resolution CT, blood and sputum culture, haematological parameters, etc) will be captured in the eCRF. It is strongly recommended to perform a full diagnostic workup, to exclude alternative causes such as lymphangitic carcinomatosis, infection, allergy, cardiogenic oedema, or pulmonary haemorrhage. In the presence of confirmatory high-resolution CT scans where other causes of respiratory symptoms have been excluded, a diagnosis of pneumonitis (ILD) should be considered and the Dosing Modification and Toxicity Management Guidelines (see the Annex document to this CSP) should be followed.

The following assessments, and additional assessments if required, will be performed to enhance the investigation and diagnosis of potential cases of pneumonitis. The results of the assessment will be collected.

- Physical examination
 - Signs and symptoms (cough, shortness of breath, and pyrexia, etc) including auscultation for lung field will be assessed.
- Saturation of peripheral oxygen (SpO₂)

Other items

- When pneumonitis (ILD) is suspected during study treatment, the following markers should be measured where possible:
 - \circ ILD markers (KL-6, SP-D) and β-D-glucan.
 - Tumour markers: Particular tumour markers that are related to disease progression.
 - o Additional clinical chemistry: C-reactive protein and LDH.

8.3 Adverse Events and Serious Adverse Events

The principal investigator is responsible for ensuring that all staff involved in the study are familiar with the content of this section.

The definitions of an AE or SAE can be found in Appendix B.

Adverse events will be reported by the patient (or, when appropriate, by a caregiver, surrogate, or the patient's legally authorised representative). For country-specific requirements for Germany see Appendix K 1.3.

The investigator and any designees are responsible for detecting, documenting, recording and reporting events that meet the definition of an AE.

8.3.1 Time Period and Frequency for Collecting AE and SAE Information

Adverse events and SAEs will be collected from time of signature of ICF, throughout the treatment period and including the safety follow-up period (30 days after last dose of study treatment for ceralasertib monotherapy or 90 days after last dose of study treatment for ceralasertib and durvalumab combination).

If the investigator becomes aware of an SAE with a suspected causal relationship to the study treatment that occurs after the end of the clinical study in a patient treated by him or her, the investigator shall, without undue delay, report the SAE to the sponsor as described in Section 8.3.12.

For patients continuing in the PTAP, AEs and SAEs will be recorded by the treating physician from the time the participant signs informed consent and will continue throughout the program until the end of the PTAP or until consent has been withdrawn. Collection and reporting of AEs and SAEs after the final DCO is described in Section 8.3.11.

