 Ceralasertib Monotherapy (Main Study)

D I	Screening a		I	ntervent	tion per	riod (28	-day cyc	cles)		Pos	st-intervention follo	Details in CSP section or appendix	
Procedure	Scree	(Cycles 1	1-2	Cycle 3			C4-onwards		t itment)	Safety follow-up	Progression/Survival Follow-up	
Cycle Day	-21 to -1	Day 1	Day 7	Day 15	Day 1	Day 7	Day 15	Day 1	Day 15	Study Treatment Discontinued (Last dose of study treatment)	30 days after last dose	(Q8W until 18 months, then Q12W)	
Visit window (± days)	-	-	-	± 1	± 3	-	± 1	± 3	± 1	(Last	± 3	± 7	
Informed consent: main study ^b	X												Section 5 and Appendix A 3
Informed consent: genetic sample and analysis (optional) ^b	X												Section 5.1 and Appendix A 3
Archival tumour sample, mandatory ^c	X												Section 8.6.1
Fresh tumour biopsy	X			X (C2 only)						X (PD)			Section 8.6.1
Inclusion and exclusion criteria e, f	X	X											Sections 5.1, 5.2 and 5.4
Demography ^g	X												Section 5.1
Prior anti-cancer therapy h	X												Section 5.1
Full physical examination ^a	X	X			X			X		X	X		Section 8.2.1
Targeted physical examination ⁱ			X	X		X	X		X				Section 8.2.1

D	Screening a		I	ntervent	tion per	riod (28	-day cyc	cles)		Pos	Details in CSP section or appendix		
Procedure	Scree	(Cycles 1	l-2		Cycle			t itment)	Safety follow-up	Progression/Survival Follow-up		
Cycle Day	-21 to -1	Day 1	Day 7	Day 15	Day 1	Day 7	Day 15	Day 1	Day 15	Study Treatment Discontinued (Last dose of study treatment)	30 days after last dose	(Q8W until 18 months, then Q12W)	
Visit window (± days)	-	-	-	± 1	± 3	-	± 1	± 3	± 1	(Last	± 3	± 7	
Height	X												Section 8.2.1
Weight a	X	X		X	X		X	X	X	X	X		Section 8.2.1
Past and current medical conditions	X	X a											Sections 5.1 and 5.2
12-lead ECG ^{j, k}	X (Trip licat e)			As clinic	ally ind	icated;	single E0	CGs					Section 8.2.3
Echocardiogram/MU GA	X			As	s clinica	ılly indi	cated			X			Section 8.2.6.1
Vital signs k	X	X	X	X	X	X	X	X	X	X	X		Section 8.2.2
ECOG performance status ¹	X	X			X			X		X			Section 8.2.4
Hepatitis B and C and HIV screening	X												Section 5.1 and 8.2.5
Safety laboratory assessments (clinical chemistry including TSH, haematology, urinalysis) ^{f, k, m}	X	X	X	X	X	X	X	Х	X	Х	X		Section 8.2.5

Procedure	Screening a		I	ntervent	tion per	riod (28	3-day cyc	cles)		Pos	t-intervention follo	Details in CSP section or appendix		
	Scree	(Cycles 1	1-2	Cycle 3			C4-onwards		t itment)	Safety follow-up	Progression/Surviva Follow-up		

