6.2.2.2 Ceralasertib Administration

Ceralasertib tablets should be taken with a glass of water. When ceralasertib is administered, patients must fast (water permitted) for at least 2 hours prior to taking a dose, to at least 1 hour post-dose for all doses.

Ceralasertib will be administered orally 240 mg twice daily, approximately 12 ± 2 hours apart, starting on Day 1 until Day 7, in each treatment cycle of both the treatment arms in the main study. In the biopsy sub-study, patients will self-administer ceralasertib tablets from Day 1 until Day 7 of Cycle 0, followed by no study treatment between Day 8 and Day 28, and from Day 1 until Day 7 Cycle 1 onwards.

Patients must receive ceralasertib for 7 days within each 28-day cycle. A cycle must not be < 28 days. Ceralasertib must not be given on any other days of the cycle, and dosing days must stay relative to Day 1 of each cycle. In case of drug interruption within the planned Days 1 to 7 dosing window (for any reason), resumption of treatment can only take place within the planned dosing window and not beyond, even if this means the patient receives less than the specified 7 days of ceralasertib dosing in the particular cycle. Dosing after Cycle Day 7 is not permitted and the planned 21 days off treatment should not be reduced.

Patients are allowed to take the scheduled dose up to 2 hours after the scheduled dose time. If the interval between two doses is more than 14 hours, then the missed dose should not be taken and the patient should continue with the next dose at the allotted time. If the patient wishes to bring forward the time of their scheduled dose, the dose can be taken up to a maximum of 2 hours prior to the scheduled time, ie, \pm 2-hour window.

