Patients should be thoroughly evaluated, and appropriate efforts should be made to rule out neoplastic, infectious, metabolic, toxin, or other etiologic causes of the imAEs. Serologic, immunologic, and histologic (biopsy) data, as appropriate, should be used to support an immune-related adverse events diagnosis. In the absence of a clear alternative aetiology, events should be considered potentially immune-related. In addition, there are certain circumstances in which durvalumab and ceralasertib should be permanently discontinued (see Section 7.1 for discontinuation criteria and the Dosing Modification and Toxicity Management Guidelines). Following the first dose of study treatment, subsequent administration of durvalumab can be modified based on toxicities observed as described in the Dosing Modification and TMG. These guidelines have been prepared by the sponsor to assist

the investigator in the exercise of his/her clinical judgement in treating these types of toxicities. These guidelines apply to AEs considered causally related to durvalumab monotherapy and durvalumab with ceralasertib regimen by the reporting investigator.

For patients who weigh > 30 kg, the dose of durvalumab cannot be modified. In case of doubt, the investigator should consult with the Study Physician. If a patient's body weight falls to 30 kg or below (≤ 30 kg) during the study, (s)he will be withdrawn from the study treatment unless (s)he derives some clinical benefit according to the treating physician. In this case, and following agreement between the treating physician and the sponsor, the patient may continue treatment at a body weight adapted dose of 20 mg/kg actual body weight.

Durvalumab dosing can be interrupted in the event of treatment-related toxicity. All toxicities will be graded according to CTCAE version 5.0. Dose reductions of durvalumab are not permitted. In case of doubt, the investigator should consult with the Study Physician.

Management of prolonged haematological toxicities

Patient should be referred to a haematologist for further investigations and management in the event of prolonged haematological toxicity such as:

- ≥ 2-week interruption/delay in study intervention due to CTCAE Grade 3 or worse anaemia and/or development of blood transfusion dependence
- \geq 2-week interruption/delay in study intervention due to CTCAE Grade 3 or worse neutropenia (ANC < 1 × 10⁹/L)

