- ≥ 2-week interruption/delay in study intervention due to CTCAE Grade 3 or worse thrombocytopenia and/or development of platelet transfusion dependence (Platelets < 50 × 10⁹/L)

Consider checking weekly differential blood counts including reticulocytes and peripheral blood smear. Bone marrow analysis and/or blood cytogenetic analysis should be considered at this stage according to standard haematological practice.

Study intervention should be discontinued if blood counts do not recover to CTC Grade 1 or better within 4 weeks of dose interruption.

Development of a confirmed myelodysplastic syndrome or other clonal blood disorder should be reported as an SAE and full reports must be provided by the investigator to AstraZeneca Patient Safety. Study intervention should be discontinued if patient's diagnosis of MDS and/or AML is confirmed.

The dose reduction levels for ceralasertib are summarised in Table 12.

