7.1.2 Follow-up of Patients Post Discontinuation of Study Treatment

After study treatment discontinuation, all patients will be followed up for safety assessments 30 days after their last dose of study treatment for ceralasertib monotherapy or 180 days after last dose of study treatment for ceralasertib and durvalumab combination (ie, the safety follow-up visit). Patients will also be followed for survival status and post discontinuation anti-cancer therapies. Additional assessments to be performed at the time of the safety follow-up are detailed in the SoA (Section 1.3). For country-specific requirements for Belgium and France see Appendices K 1.1 and K 1.2, respectively.

Patients who have discontinued study treatment prior to objective RECIST 1.1-defined radiological progression will be followed up with tumour assessments according to the SoA until RECIST 1.1 defined disease progression or death regardless of whether or not the patient started a subsequent anti-cancer therapy, unless they have withdrawn all consent to study related assessments.

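### Monotherapy AE collection and the 30-day safety visit run from the last ceralasertib dose, so after a delayed cycle start both can be over before treatment is formally stopped

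*Protocol*

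**What the plan says.** For monotherapy, Protocol 8.3.1 collects AEs and SAEs from consent, across treatment, and then through a safety follow-up ending "30 days after last dose of study treatment for ceralasertib monotherapy". Section 7.1.2 sets the safety visit "30 days after their last dose of study treatment for ceralasertib monotherapy". Table 2 in Section 1.3 heads one column "Study Treatment Discontinued (Last dose of study treatment" and places the 30-day visit (±3 days) after it. Section 9.4.3.1 ends the treatment-emergent period 30 days after the last dose, or earlier if another cancer therapy starts.

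The schedule is intermittent. Section 6.2.2.2 says "Patients must receive ceralasertib for 7 days within each 28-day cycle" and adds "Dosing after Cycle Day 7 is not permitted and the planned 21 days off treatment should not be reduced". Section 6.6.1 ends treatment if blood counts have not recovered to Grade 1 or better "within 4 weeks of dose interruption".

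The sentence on late related SAEs in 8.3.1 covers only events after the study itself has ended. Under 8.3.2, AEs still open at a patient's last study visit are followed without eCRF entry.

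**The concern.** With daily dosing, last dose and discontinuation nearly coincide, and one column can serve for both. With 7 days on and 21 off, a decision taken when the next cycle is due comes three weeks after the last dose. A decision taken after a cytopenia hold comes later still. No passage restarts the 30 days at that decision.

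Two things are at stake. First, a patient stopped after a long hold reaches the discontinuation visit when the 30-day visit is already past, so the sequence in Table 2 cannot be carried out. Second, a new non-fatal event soon after such a stop, such as an infection or a bleed, falls outside the collection window of 8.3.1. It also falls before the study-end point from which the late-SAE sentence applies. Anaemia, neutropenia and thrombocytopenia are identified ceralasertib risks (2.3.1.1), and the prolonged-cytopenia guidance in 6.6.1 was added in the current amendment without any change to this window.

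**Working it through.** **Inputs.** Dosing on 7 of 28 days, none after cycle Day 7 (6.2.2.2). Window and visit 30 days after last dose (8.3.1, 7.1.2, Table 2). Scans every 8 weeks ±1 week from Cycle 1 Day 1 (8.1.1). Stop rule at 4 weeks of interruption (6.6.1).

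**The plan's own figure.** Days off per cycle = 28 − 7 = 21, as stated in 6.2.2.2.

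**Formula.** With the last dose on cycle Day 7, the window ends on Day 7 + 30 = 37. For a stop decided on cycle day *d*, days since last dose = *d* − 7 and days left = 37 − *d*. The next cycle is due on Day 29. Eight weeks is two 28-day cycles, so on an undelayed schedule the 8-weekly scan falls on a next-cycle Day 1.

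| Stop decided at | *d* | Days since last dose | Days left |
|---|---|---|---|
| Day 15 visit | 15 | 8 | 22 |
| Scan one week early | 22 | 15 | 15 |
| Next cycle due | 29 | 22 | 8 |
| Scan one week late | 36 | 29 | 1 |
| Next cycle delayed 4 weeks | 57 | 50 | −20 |

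Day 37 is 8 days after the due date (37 − 29), so the window has closed once a delay reaches 9 days.

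**Visit order.** The 30-day visit, with its ±3 days, falls 27 to 33 days after the last dose. A stop at 4 weeks' delay is 50 days after it, so the visit was due at least 50 − 33 = 17 days before the discontinuation visit.

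**Sensitivity to when the 4 weeks start.** If they run from a cytopenia found on Day 15, they end on Day 15 + 28 = 43, and 37 − 43 = −6. If dosing is interrupted inside Days 1 to 7 with the last dose on Day *L*, the interruption starts on *L* + 1 and reaches 4 weeks on *L* + 29. The window ends on *L* + 30, so 1 day is left. The maximum interruption in Section 6.6 is redacted and the content of Table 11 is not shown, so the 4-week figure rests on 6.6.1 alone.

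**What still applies after the stop.**
- 6.6: a patient stopped for unresolved toxicity is observed until it clears.
- 8.2.5: Grade 3 or 4 laboratory values at discontinuation are followed to Grade 1 or 2.
- 6.6.1: confirmed MDS is reported as an SAE.
- 8.3.9: a death from late toxicity after the follow-up period is reported as an SAE.
- 8.3.12 asks for any SAE arising during the study, and Appendix B 2 counts follow-up as a study phase. Read broadly, these reach SAEs after day 30, but they then do not match the window in 8.3.1.

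None of these sets a rule for recording a new non-serious AE after a late stop.

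**The case against.** The strongest reply is that counting from last exposure is a usual and defensible choice. Every patient gets 30 days after the last dose, and 4.3.1 cites a model in which platelets and neutrophils need at least two weeks off drug to recover. That stands: the anchor is not an error in itself.

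The second reply is that 8.3.1 also collects events during treatment, and a patient on hold has not been discontinued. On that natural reading, the cytopenia and anything else before the decision are recorded. This largely stands, although the protocol does not say that a hold is treatment period. It does not help with events after the decision.

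A reader might infer more than the documents support:
- **That patients stopped for severe toxicity get no safety follow-up.** Sections 6.6 and 8.2.5 require observation and laboratory follow-up, and Table 2 has assessments at discontinuation. What is missing is defined event recording.
- **That the 2-week haematology referral falls in the gap.** The trigger ("2-week interruption/delay in study intervention due to CTCAE Grade 3 or worse anaemia") is not a stop. A patient on hold is plausibly still in the treatment period.
- **That all of the roughly 50 monotherapy patients are affected.** A stop at a Day 15 visit leaves 22 days, and a stop during dosing leaves nearly all 30.
- **That the 8.3.2 limit on eCRF entry starts at day 30.** It refers to the last visit in the study, and patients stay in progression and survival follow-up.
- **That the safety profile is materially understated.** Nothing in the protocol lets that bias be sized. Moving the collection window alone would not change the summary tables either, because 9.4.3.1 has its own 30-day limit.

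**Conclusion.** The point holds in a limited form. Table 2 joins two dates that this schedule separates. About 8 of the 30 days remain after a stop when the next cycle is due (1 to 15 with the scan window). After a 4-week delay of the next cycle start, the decision comes about 20 days after collection and the safety visit have passed. If the interruption began inside Days 1 to 7, about 1 day remains.

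The consequence is a gap in the defined recording of new AEs, and arguably of non-fatal related SAEs, after a delayed stop, plus a visit sequence that cannot be followed. The figures assume the last dose was on Day 7, except in the interruption case, and that the 4 weeks run from the due date. The gap concerns only monotherapy patients stopped late in, or after, a cycle. The summary of changes says the study no longer recruits, so a change reaches only those still on treatment or in follow-up. It is worth making because it is cheap and improves safety capture.

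**What to change.** 1. In 8.3.1, widen the late related-SAE sentence so that it applies at any time after the safety follow-up period, not only after study end, and reconcile it with 8.3.12.
2. In Table 2, 7.1.2 and 8.3.1, record the last-dose date and the permanent-discontinuation date separately. State that a dose hold is part of the treatment period. Schedule monotherapy AE/SAE collection and the safety visit so that neither ends before the discontinuation visit, for example 30 days from the later of the two dates. The synopsis and Appendices K 1.1 and K 1.2 repeat the 7.1.2 sentence and need the same change.
3. In 9.4.3.1, align the treatment-emergent period, or report the added events separately and keep the summary to 30 days after last dose for comparison between arms.

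The cost is wording, a few more recorded AEs, and a later visit for some patients. Under the example rule the visit would fall 22 + 30 = 52 days after the last dose for a stop when the next cycle is due, and 50 + 30 = 80 days after it for a stop at 4 weeks' delay. That is 22 and 50 days later than now. No dose or stopping rule changes.
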